12 STATISTICAL CONSIDERATIONS

12.1 Study Hypotheses

- 1. The AMI-PM will produce better short term (T1) clinical outcomes than the Campaign (CA+PM) (AIM 1).
- 2. The CA+PM+AMI-PM will produce better mid-term (T2) and long-term (T3) clinical outcomes than the AMI-PM+CA+PM (AIM 2).
- 3. The AMI-PM will produce more change in mediating cognitive domains than the CA+PM.
- 4. Both AMI-PM+CA+PM and CA+PM+AMI-PM will result in no differences in change in mediating cognitive domains from T0 to T2.
- The greater the dosage (proportion of total talking points recorded for all domains in a tailored AMI; and exposure to campaign activities and messages), the better the outcomes.
- 6. We will investigate an exploratory hypothesis examining the effects of the intervention and sequence on oral health quality of life (a secondary outcome), as well as on clinical outcomes.

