12.2 Sample Size Considerations

Sample size calculations are based on the primary outcomes of continuous measures of the Gingival Index and Plaque Scores using estimates of effect and variation from the pilot grant. The MFFD design has two sequences, called A:B and B:A, and two periods (1 and 2). We will power on the first period, which is essentially a two-arm parallel design with randomization at the building level. The study design will recruit N=60/building, with 3 buildings on sequence A:B (N=180) and three on sequence B:A (N=180).

Table Sample size for a two-group t-test, using a two-sided α =0.05						
Outcome	Source	Mean	Std Dev	Effect	N per	Power
		difference		Size	group	
Plaque Index	Pilot	0.25	0.34 (pilot)	0.74	123	99
Gingival Score	Pilot	0.66	0.60 (pilot)	1.1	123	99
Plaque Index	Pilot	0.25	0.47 (UCL)	0.53	123	98
Gingival Score	Pilot	0.66	0.81 (UCL)	0.82	123	99
Plaque Index	Pilot*.75	0.20	0.47 (UCL)	0.42	123	91
Gingival Score	Pilot*.75	0.50	0.81 (UCL)	0.62	123	99
UCL= Upper 95% CL of the pilot study SD						

Attrition: Longitudinal studies must account for attrition. If we assume a conservative 75% retention rate across the study that would leave us with approximately N=135 per intervention group, or N=45 per building.

Effects of intra-class correlation (ICC) within sites: The cluster design can sometimes impact the power of a study and our calculations consider this human phenomenon. To account for the cluster design, we calculated the effective sample size which is the sample size used for power calculations, according to Killip et al. With this design we expect to have 6 clusters of N=45 each finish the study, or 135 per sequence. Assuming an intracluster correlation coefficient (ICC) of 0.01 or 0.02, which are typical values for human subject studies, this gives effective sample sizes closer to 123. The strategy therefore is to accordingly adjust the sample sizes used in calculations. As a result, our sample size calculations are based on a maximum number of N=123 per intervention (not 135) after accounting for loss of power due to intra-class correlation. Using N=123 per group, our power ranged from 91 to 99 for different scenarios reflecting varied assumptions, as shown in the attached memo from September 5, 2016.

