Intervention variables: As all subjects are exposed to the same interventions, it is of interest to unpack the intervention into 1) dosage (percent of talking points covered for all focal points (domains) addressed in the intervention, and 2) exposure to focal point messages during campaigns. Study Hypothesis #5, regarding dosage of interventions, will be assessed by creating an ordinal scale that measures an individual's exposure to talking points through participation in the AMI and exposure to messages via campaigns, thus creating a measure of dosage. We will then assess if dosage predicts better outcomes. This can be done directly (e.g., compare mean gingival scores across dosage levels with ANOVA) or dosage can be used as a predictor variable in the statistical models and causal pathway analyses. Oral health skills/Practice-to-Mastery (a 4 point Likert scale) and focal points (count variable) can be analyzed using similar techniques and approaches.

MFFD layout: N at the beginning of study			
	Sequence	N	
Building 1	A:B	60	
Building 2	B:A	60	
Building 3	A:B	60	
Building 4	B:A	60	
Building 5	A:B	60	
Building 6	B:A	60	

Secondary Outcome of General Oral Health Assessment Inventory (GOHAI): We will conduct a set of secondary analyses with GOHAI as a continuous outcome. It will also be incorporated into our statistical/mediator models as predictor to see if it acts as an effect modifier.

Cognitive Mediators: The following variables will be incorporated into the causal pathway analysis to address example hypotheses #3 and #4: knowledge, oral health beliefs/norms, social support, oral hygiene behaviors, fears/worries, practice to mastery, and behavioral intentions. We will use longitudinal mediation to compared the efficacy of AMI-PM+CA+PM to CA+PM+AMI-PM in terms of whether they differ significantly in the amount of change that they engender in the gingival index and plaque score, indirectly through the mediators measured in our model.

outcomes.

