To test hypothesis #4, we will conduct dynamic mediation using latent change (difference) score (LCS) mediation analysis. The analyses will be conducted in Mplus 7 where change (difference) scores representing differences in each mediator and outcome variable from baseline to final follow up (i.e. T1-T0 (ΔT_{10}), and T2-T1(ΔT_{21}) will be generated. It is the difference scores of the mediators and outcome variables that are modeled. Generally speaking, causal paths specifying latent (true) change, represented by change in knowledge, oral health beliefs/norms, OH social support, oral hygiene behaviors, fears/worries, oral health practice to mastery skills, and behavioral intentions in going from T0 to T1, and T1 to T2 will be specified, to predict change in Gingival Index and Plaque Scores at T2 (i.e., ΔGingival Index₂₁, ΔPlaque score₂₁). For example, we will test whether change in fears/worries from T0 to T1 significantly predicts changes in Gingival Index and Plague Scores at final follow-up, T2 (ΔGingival Index₂₁, Δ Plague scores₂₁). To assess the impact of the change in self-efficacy (Δ SE). on changes in Gingival Index scores (ΔGingival Index), direct and indirect paths from change in self-efficacy from baseline to first follow up (ΔSE₁₀) that predict the change in Gingival Index at the final follow-up (ΔGingival Index₃₀) will be specified and tested. Select direct and indirect paths from change scores of the other mediator variables to change scores of behavioral outcomes will also be specified in a similar fashion, and all these relationships will be tested simultaneously.

Summary: Using a conservative set of assumptions and based on our own pilot data, we have demonstrated, using our pilot data estimates, that we will have sufficient power to detect significant changes, using a two-group t-test which makes minimal

IRB Review
IRB NUMBER: 14-188-6
IRB APPROVAL DATE: 01/03/2019
12/14/2018

Good Oral Health: A Bi-level Intervention to Improve Older Adult Oral Health Protocol #14-046-E

assumptions about the data. It is worth noting that the proposed statistical models have greater power characteristics than the t-tests used to calculate power.

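### Hypothesis 4 predicts no difference between sequences in mediator change, but the plan states no rule that could support such a claim

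*Combined protocol and SAP*

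**What the plan says.** Section 12.1 lists as Hypothesis 4 that "Both AMI-PM+CA+PM and CA+PM+AMI-PM will result in no differences in change in mediating cognitive domains from T0 to T2". The research prediction is therefore itself a null.

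Three places in Section 12.4 bear on how it would be assessed:

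- The Cognitive Mediators paragraph says that the listed mediators "will be incorporated into the causal pathway analysis to address example hypotheses #3 and #4". It then compares the two sequences by "whether they differ significantly in the amount of change that they engender in the gingival index and plaque score, indirectly through the mediators".
- The paragraph naming the test begins "To test hypothesis #4, we will conduct dynamic mediation using latent change". It goes on to describe paths from change in the mediators to change in Gingival Index and Plaque Score. It states no pass/fail criterion for similarity of the two sequences.
- A latent change score model with AMI and Campaign as predictors of mediator change is described, but it is assigned to Hypothesis 3. It too has no margin or decision rule.

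Section 12.2 does not size the trial for this question: "Sample size calculations are based on the primary outcomes of continuous measures of the Gingival Index and Plaque Scores". The test is a superiority t-test "using a two-sided α =0.05", and "We will power on the first period, which is essentially a two-arm parallel design with randomization at the building level". Hypothesis 4 concerns change to T2, after both periods. The documents give no equivalence margin, smallest important mediator difference, SD of mediator change or ICC for the mediators.

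**The concern.** A prediction of no difference needs a rule that imprecise data cannot satisfy. Here the only between-sequence yardstick is statistical significance, so the likely practice is to treat a non-significant comparison as agreement with Hypothesis 4. Smaller samples, more dropout or noisier scales would then make the hypothesis easier to support. Changing the model does not cure this, because any significance test used this way has the same property.

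The stake is a published statement that the order of the components makes no difference to the cognitive domains, resting on an interval wide enough to include differences the investigators would care about.

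There is also a mismatch of quantity. The hypothesis concerns change in the mediators. The significance sentence concerns clinical change passing through them, and the named model concerns how mediator change predicts clinical change. No stated analysis directly compares the sequences on the quantity in Hypothesis 4.

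**Working it through.** **Inputs from the plan (Section 12.2).** Six buildings, three per sequence; 60 recruited and 45 expected to finish per building, so 135 per sequence; ICC 0.01 or 0.02; 123 per group used for power; two-sided alpha 0.05. The 45 is the projection to T3 (Section 4 gives about 270 in total by then), so T2 numbers may be higher.

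**Assumptions (not in the plan).** True sequence differences of 0.2 and 0.3 SD of mediator change; equivalence margins of 0.3 and 0.5 SD; the plan's ICCs carried over to the mediators; one mediator at a time.

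**Step 1: reproduce the plan's own figure.** Lowest-power row: 0.20/0.47 = 0.426; 0.426 × √(123/2) = 3.34; power = Φ(3.34 − 1.96) = 91.6% (91.4% with the t distribution), against 91 stated. The other five rows also reproduce. This is power for clinical outcomes in Period 1; no figure is given for Hypothesis 4.

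**Step 2: effective sample size.** 135/(1 + 44 × 0.01) = 93.75, about 94; 135/(1 + 44 × 0.02) = 71.8, about 72. The plan's 123 would need an ICC of (135/123 − 1)/44 = 0.0022. Results are shown at all four sizes.

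**Step 3: chance of non-significance when a difference exists.** This is 1 minus the power of a two-sided 0.05 t-test with noncentrality d√(n/2), on 2n − 2 df, or on 4 df (6 buildings − 2 sequences, ignoring the pairing). Example: n = 123, d = 0.3 gives 0.3 × √61.5 = 2.35; Φ(1.96 − 2.35) = 34.7%, or 35.1% with the t distribution.

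| Per arm | 95% CI half-width, 1.96√(2/n) | d = 0.2 | d = 0.3 | d = 0.3, 4 df |
|---|---|---|---|---|
| 135 (no clustering) | 0.24 SD | 63% | 31% | 53% |
| 123 (plan) | 0.25 SD | 65% | 35% | 57% |
| 94 (ICC 0.01) | 0.29 SD | 72% | 47% | 65% |
| 72 (ICC 0.02) | 0.33 SD | 78% | 57% | 72% |

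At d = 0.2 with 4 df the range is 75-85%. Fewer data raise the figure: at d = 0.3 it goes from 35% at 123 per arm to 63% at 60 and 79% at 30.

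**Step 4: sensitivity to T2 retention.** With nobody lost there are 180 per arm, or 180/(1 + 59 × 0.01) = 113 and 180/(1 + 59 × 0.02) = 83 effective. At d = 0.3 the normal approximation gives Φ(1.96 − 0.3√90) = 19%, Φ(1.96 − 0.3√56.6) = 38% and Φ(1.96 − 0.3√41.3) = 51%. The problem shrinks but remains.

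**Step 5: what a proper rule could show.** Two one-sided 5% tests (90% CI inside the margin), true difference zero: power = 2Φ(margin/√(2/n) − 1.645) − 1. Example: n = 135, margin 0.3 gives 2Φ(0.3/0.1217 − 1.645) − 1 = 59%.

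| Per arm | Margin 0.3 SD | Margin 0.5 SD |
|---|---|---|
| 135 | 59% | 99% |
| 123 | 52% | 98% |
| 94 | 32% | 92% |
| 72 | 12% | 82% |

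Simulated with 4 df at 123, 94 and 72 per arm: 34%, 23% and 14% for 0.3 SD; 88%, 76% and 61% for 0.5 SD. These are generally lower. The exception is 72 per arm at 0.3 SD, where both figures are very low.

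**The case against.** The strongest objection is that the plan never says a non-significant result supports Hypothesis 4. The significance sentence concerns gingival and plaque change acting through the mediators, and the model named for Hypothesis 4 has no pass/fail rule. A reader might infer that the plan adopts a wrong rule. The documents support only that it adopts none. This part of the objection stands, and it narrows the point. It does not remove it, because a no-difference hypothesis with no rule leaves significance as the only yardstick in sight.

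A reader might also infer that primary objective 3 is undermined. The documents do not support this. That objective (Section 3.1) asks whether cognitive and behavioral factors mediate clinical change. Equal mediator change in the two sequences would neither establish nor refute that. The clinical sequence question is Hypothesis 2, which is directional and has its own repeated-measures analysis.

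Nor can one say that a finding of no difference would arise mainly because there are only six buildings. At 135 per arm without clustering, a 0.3 SD difference would be detected 69% of the time (100 − 31).

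Finally, the sizes depend on assumed differences and margins, and 45 per building is a T3 figure. Both are fair limits. At a 0.5 SD margin the design could support an equivalence claim reasonably well, so the outlook depends on a margin the plan has not chosen.

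**Conclusion.** The concern holds as a missing decision rule for a hypothesis of no difference, not as a misstated one. As written, imprecision can read as support for Hypothesis 4. With an assumed true difference of 0.3 SD and up to 45 completers per building, that would happen in 31% to 57% of trials by person-level or ICC-adjusted tests. At effective sizes of 94 to 72 with 4 building-level df it would happen in 65% to 72%. With full retention at T2 and no clustering, the most favorable case shown, it is still about 19%. Whether the trial could show equivalence depends on the margin: at the plan's 123 per arm, normal-approximation power is 52% for 0.3 SD and 98% for 0.5 SD.

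These sizes rest on assumed differences, margins and mediator ICCs. The logical gap does not. It concerns a mediator hypothesis, should be corrected before analysis, and leaves the primary clinical comparisons untouched.

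**What to change.** In Sections 12.1 and 12.4:

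- Estimate the between-sequence difference in T0-T2 change directly for each cognitive domain, with a 90% CI that accounts for building and its limited degrees of freedom.
- Conclude no meaningful difference in a domain only if that CI lies wholly inside a margin fixed and justified by the investigators before analysis. Otherwise report the domain as inconclusive.
- Name the SD that scales the margin (baseline or change), and say whether Hypothesis 4 requires every domain to meet it.
- State that p > 0.05 does not support Hypothesis 4.

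Alternatively, restate Hypothesis 4 as estimation of the sequence difference with CIs and drop the prediction of no difference.

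Either change needs wording only: no added visits, data or participants. The downside is that the result may be inconclusive, which is likely with a tight margin such as 0.3 SD once clustering is allowed for.

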12.2 Sample Size Considerations

Sample size calculations are based on the primary outcomes of continuous measures of the Gingival Index and Plaque Scores using estimates of effect and variation from the pilot grant. The MFFD design has two sequences, called A:B and B:A, and two periods (1 and 2). We will power on the first period, which is essentially a two-arm parallel design with randomization at the building level. The study design will recruit N=60/building, with 3 buildings on sequence A:B (N=180) and three on sequence B:A (N=180).

Table Sample size for a two-group t-test, using a two-sided α =0.05						
Outcome	Source	Mean	Std Dev	Effect	N per	Power
		difference		Size	group	
Plaque Index	Pilot	0.25	0.34 (pilot)	0.74	123	99
Gingival Score	Pilot	0.66	0.60 (pilot)	1.1	123	99
Plaque Index	Pilot	0.25	0.47 (UCL)	0.53	123	98
Gingival Score	Pilot	0.66	0.81 (UCL)	0.82	123	99
Plaque Index	Pilot*.75	0.20	0.47 (UCL)	0.42	123	91
Gingival Score	Pilot*.75	0.50	0.81 (UCL)	0.62	123	99
UCL= Upper 95% CL of the pilot study SD						

Attrition: Longitudinal studies must account for attrition. If we assume a conservative 75% retention rate across the study that would leave us with approximately N=135 per intervention group, or N=45 per building.

Effects of intra-class correlation (ICC) within sites: The cluster design can sometimes impact the power of a study and our calculations consider this human phenomenon. To account for the cluster design, we calculated the effective sample size which is the sample size used for power calculations, according to Killip et al. With this design we expect to have 6 clusters of N=45 each finish the study, or 135 per sequence. Assuming an intracluster correlation coefficient (ICC) of 0.01 or 0.02, which are typical values for human subject studies, this gives effective sample sizes closer to 123. The strategy therefore is to accordingly adjust the sample sizes used in calculations. As a result, our sample size calculations are based on a maximum number of N=123 per intervention (not 135) after accounting for loss of power due to intra-class correlation. Using N=123 per group, our power ranged from 91 to 99 for different scenarios reflecting varied assumptions, as shown in the attached memo from September 5, 2016.

Calculation for Primary Outcomes: While the pilot data provide a good starting point for sample size estimation, we acknowledge that the study was small and the results provide only estimates. To be conservative regarding pilot results, we 1) decreased the observed effect size by 25% and 2) used the upper 95% CL of the standard deviation for calculations. Employing these two hedges gives protection and helps assure we will have sufficient power to detect similar (or smaller) effect sizes with 80% power. With N=135 per group our study still has more that 90% power to find detect the mean differences (MD) in the table below.

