Our successful pilot intervention Changing Oral Health Norms and Hygiene Practices among Vulnerable Older Adults supported by NIDCR #R34 DE022271 (2011-2013) was based on Fishbein's modified theory of reasoned action called Integrated Model (IM) of Behavioral Prediction (Fishbein, 2008) operationalized through Adapted Motivational Interviewing (AMI) and Bandura's notions of self-efficacy and skills reinforcement operationalized through Practice-to-Mastery or PM (Liska, 1984; Connor, 2010). The pilot study was conducted in a single building of approximately 200 apartments in the Greater Hartford Area. It included two components offered sequentially, a face to face intervention (the AMI) with practice of oral hygiene skills to mastery (PM), and two campaign fairs promoted by a small committee of building residents. Post intervention, participants (n=30) demonstrated a significant improvement in the Plague Scores from a mean score at baseline of 84% (sd=11.8%) to 58% (sd=31.2%) at follow-up (p<0.001) and the Gingival Index from a mean baseline score of 1.2 (sd=0.56) to a mean follow-up score of 0.54 (sd=0.47), p<0.001. Differences in P-M skills scores from pre to post instruction in brushing and flossing, part of the AMI-PM session showed significant improvement. Brushing scores increased from 1.9 (fair/poor) prior to the AMI-PM session to 2.9 (good/excellent; p<0.001) after and flossing skills improved from 1.7 to 2.7 (p<0.001). In the intervention group, we found significant mean decreases (improvements) from pre to post in several important cognitive domains including perceived risk of oral disease which decreased from a mean of 2.5 to 2.0 (sd=.70 for both, p=.04) self-management worries which decreased from a mean of 1.36 (sd=.66) to 0.57 (sd=.97); p=.002) and self-management fears which decreased from a mean of 2.2 (sd=.81) to 1.53 (sd=.97; p=.001). In contrast, non-AMI respondents showed mean increases (deterioration) from pre to post in all three domains.

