The pilot intervention evaluated the outcomes of both intervention components together. The proposed study uses a modified fractional factorial design (MFFD), a design approach developed to maximize capacity and cost effectiveness of testing intervention designs with multiple components which are found to be effective, but in which the interactivity of the components to produce positive outcomes is not well understood (Chakraborty, Collins, Strecher, Murphy, 2009; Collins, 2013; Nair, Strecher, Fagerlin, Ubel, Resnicow, Murphy, et al. 2008; Collins, Dziak, Li, 2009; Collins, Murphy, Nair, Strecher, 2005). Thus, the study is designed to evaluate the face to face and campaign components against each other, and in different additive sequences to determine which component has better short term outcomes, and whether sequencing components makes a difference in the final outcome.

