The pilot study on which the current protocol is based was structured as a bi-level intervention, delivered at the individual and at the "building" level. The pilot intervention was delivered as a "package" without differentiating the contributions of each component to the outcomes. Further, the pilot study did not allow us to assess whether the order of administration of the main components (individual versus group/community) made a difference in outcome. The study sample was too small to explore fully the

interaction of cognitive and behavioral domains in contributing to clinical outcomes. The design of the proposed expansion study will allow us to address these limitations.

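### Section 12.2 powers AMI-PM versus CA+PM with the pilot's one-group before-after change under both components, so the 91–99% power is not supported for Hypothesis 1, mainly for plaque

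*Combined protocol and SAP*

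**What the plan says.** Section 12.2 bases the sample size on the two primary outcomes, "using estimates of effect and variation from the pilot grant". It adds: "We will power on the first period, which is essentially a two-arm parallel design with randomization at the building level". Hypothesis 1 (section 12.1) and the Period 1 paragraph of section 12.4 identify that comparison as AMI-PM against the campaign at T1.

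The power table uses a two-group t-test, two-sided 0.05, with 123 per group. Its mean differences are 0.25 for plaque and 0.66 for GI, then 0.20 and 0.50 in the rows reduced by 25%. The text concludes that "our power ranged from 91 to 99 for different scenarios reflecting varied assumptions".

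Section 2.1 reports the pilot results for 30 participants after the intervention. Plaque went "from a mean score at baseline of 84% (sd=11.8%) to 58% (sd=31.2%) at follow-up". The other result was "the Gingival Index from a mean baseline score of 1.2 (sd=0.56) to a mean follow-up score of 0.54 (sd=0.47), p<0.001". On what was tested, section 2.1 says: "The pilot intervention evaluated the outcomes of both intervention components together". Section 2.2 adds that the pilot was delivered "without differentiating the contributions of each component to the outcomes".

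**The concern.** The power table needs the difference between two arms that both receive an active component. The pilot supplies something else: how far one group moved from baseline after receiving both components. That movement contains the effect of AMI-PM, the effect of the campaign and any change unrelated to either.

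CA+PM is not an inert control. It delivers messages on the same domains and includes practice to mastery, and Hypothesis 5 expects more campaign exposure to give better outcomes. Unless AMI-PM alone outperforms the full package, the gap can equal the whole package change only if CA+PM produces no change.

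A reader will take 91–99% as the chance of detecting a real AMI-PM advantage on either primary outcome. If power for plaque is much lower, a null plaque result at T1 could be misread as showing that the two components work equally well. Which component has the better short-term outcome is one of the questions the study was set up to answer.

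**Working it through.** **Inputs.** Section 12.2: n = 123 per group; two-sided α = 0.05; SDs 0.34 (pilot) and 0.47 (upper limit) for plaque, 0.60 and 0.81 for GI; mean differences 0.25 and 0.66. Section 2.1: pilot means before and after.

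**Step 1: source of the differences.**
- GI: 1.2 − 0.54 = 0.66, exactly the table value.
- Plaque: 0.84 − 0.58 = 0.26, against 0.25 in the table.

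**Step 2: reproduce the plan's power.** Power is taken from the noncentral t distribution with df = 2 × 123 − 2 = 244 and noncentrality δ = D / (SD × √(2/n)), where √(2/123) = 0.1275. For the least favourable row, D = 0.20 and SD = 0.47 give δ = 0.20 / 0.0599 = 3.34 and power 91.4% (plan: 91). Also, 0.25/0.47 gives 98.6% (plan: 98) and 0.50/0.81 gives 99.8% (plan: 99). The remaining three rows exceed 99.9%. The table's arithmetic is sound.

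**Step 3: what those differences imply.** Suppose AMI-PM alone achieves the full package change. A GI gap of 0.66 then requires CA+PM to achieve 0.66 − 0.66 = 0. The reduced gap of 0.50 requires 0.66 − 0.50 = 0.16, about a quarter of the package change.

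**Step 4: power at other gaps.** The documents give no expected AMI-PM minus CA+PM clinical difference, so the gap is an assumed fraction of the table's 0.25 and 0.66. Same formula, n = 123:

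| Gap, fraction of package change | Plaque D | Power, SD 0.34 / 0.47 | GI D | Power, SD 0.60 / 0.81 |
|---|---|---|---|---|
| 75% | 0.1875 | 99.1% / 87.6% | 0.495 | >99.9% / 99.8% |
| 50% | 0.125 | 81.9% / 54.7% | 0.33 | 99.0% / 88.9% |
| 25% | 0.0625 | 30.0% / 18.0% | 0.165 | 57.5% / 35.6% |

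The table's reduced plaque row uses 0.20, which is 80% of 0.25. An exact 25% cut is 0.75 × 0.25 = 0.1875, so it shows 91% where the exact cut gives 88%. Starting from 0.26 raises plaque power at the 50% gap to 85–58%.

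**Step 5: minimum detectable difference.** At 80% power and n = 123 the standardized difference is 0.3587.
- Plaque: 0.3587 × 0.34 = 0.122 and 0.3587 × 0.47 = 0.169, or 49% and 67% of 0.25.
- GI: 0.3587 × 0.60 = 0.215 and 0.3587 × 0.81 = 0.291, or 33% and 44% of 0.66.

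**Step 6: dependence on n.** The figure of 123 is the plan's own. The usual design effect with the stated ICCs gives 135 / (1 + 44 × 0.01) = 94 and 135 / (1 + 44 × 0.02) = 72. At the 50% gap with upper-limit SDs, power is then 44% and 35% for plaque, and 79% and 68% for GI, before any allowance for having only six buildings.

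**The case against.** - **The plan already hedges.** It cuts the pilot effect by 25% and uses the upper confidence limit of the SD. The reason given is that "we acknowledge that the study was small and the results provide only estimates". That addresses imprecision in the pilot estimate, not its use for a different contrast.
- **A rationale may lie elsewhere.** Section 12.2 cites a memo of September 5, 2016 that is not in the documents available. This limits what can be said about the source of 0.25, and about whether a rationale was recorded there. Section 2.2 says published studies also inform the effect sizes, but gives no figures, and the table names only the pilot as source.
- **The low plaque figure combines an assumed gap with a pessimistic SD.** This stands. With the pilot SD, half the package change leaves plaque at 82%; with the pilot's follow-up SD of 0.312 it is about 88%. That is why both ends of the range are shown and the fraction is labelled an assumption.
- **The planned models may have more power than a t-test,** as the section 12.4 summary says. Better precision would not supply the missing between-arm difference.
- **No equivalence claim is planned for the clinical outcomes at T1.** True. Misreading a null result would be an error of interpretation, though the stated power would encourage it.
- **The reassurance on GI depends on n = 123.** This stands, as Step 6 shows.

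**Conclusion.** The concern holds. The stated 91–99% is right for the differences printed beside it, but the pilot did not estimate those differences as gaps between AMI-PM and CA+PM. The match is exact for GI; for plaque it is within 0.01, with the memo unseen.

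At the plan's 123 per group, 80% power requires the between-arm gap to be at least 49–67% of the pilot change for plaque and 33–44% for GI. Plaque is therefore the more exposed outcome, and GI is fairly robust only at that sample size. The true gap is unknown. The power figures for particular gaps rest on assumed fractions and on the plan's own SDs and t-test. The fault weakens the power justification for Hypothesis 1; it does not invalidate the trial or its analysis.

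**What to change.** In section 12.2:

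1. State that 0.66 is, and 0.25 appears to be, a pilot before-after change under the combined package, and that neither estimates the AMI-PM minus CA+PM difference at T1. If the memo gives another source for 0.25, cite it.
2. Replace the 91–99% claim for Hypothesis 1 with the minimum detectable AMI-PM versus CA+PM difference at 80% power for each outcome. At 123 per group this is 0.122–0.169 for plaque and 0.215–0.291 for GI.
3. Add power at gaps of 25%, 50% and 75% of the package change, under both the pilot SD and the upper-limit SD.
4. Compute items 2 and 3 with whatever effective sample size is adopted once the ICC adjustment has been checked.

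The cost is a wording change and one recomputed table. Enrolment and analysis stay as they are. The stated power becomes less favourable, chiefly for plaque.
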